6.0 Study Agent Administration and Safety

Oxandrolone Administration

Oxandrolone will be given to experimental men (12 mg BID) and women (6 mg BID) for 12 weeks starting the day of surgery. Previous clinical studies where oxandrolone was given for greater than 6 months have shown no androgenic effects, behavioral changes, sepsis, hirsutism, or acne in the patient population. Elevated liver transaminase levels have been noted but have been transient and asymptomatic.¹⁻³

Patient Safety and Compliance

Patients will have liver transaminase levels measured when preoperative labs are obtained. Additionally, liver enzymes will be assessed at 2, 6, 12, and 24 weeks after rotator cuff repair. Testosterone levels and a quantitative assay for oxandrolone will also be drawn prior to supplementation, at the 2 week post-operative visit and at the 6 month post-operative visit to assess for compliance. Any adverse medication reaction will be met with cessation of medication, but will continue to be followed for outcome data collection.

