7.0 Clinical and Laboratory Evaluations

Program Time Line

Study participants will be tested on multiple occasions. Information will be collected prior to surgery, followed by measurements on the day of procedure, and 2, 6, 12, 24, 52, and 104 weeks after surgery. Surgery will be performed on an arranged date with the orthopaedic surgeon. Physical therapy will follow a pre-defined protocol with a physical therapist.

Testing Visits

Outcome measures and safety measures will be collected at routine postoperative visits with the operating surgeon. Dates and involved events are described in Table 1 below.

Schedule of Events

Event	Pre-Procedure	Procedure Day	Post-Operative Week					
			2	6	12	24	52	104
Informed Consent	x							
Demographics	x							
Confirm Inclusion/Exclusion Criteria	x	x						
Medical History	x	x						
Vital Signs	x	x	x	x	x	x	x	x
Randomization		x						
Blood draw: Testosterone level and Oxandrolone level	x		x			x		
Blood draw: Liver Enzymes	x		x			x	x	x
Outcomes:								
MRI: rotator cuff healing; Sugaya classification (primary outcome)	x				x		x	x
MRI: Fatty infiltrate (secondary outcome)	x				x		x	x
MRI: Muscle volume (secondary outcome)	x				x		x	x
Body Composition – lean mass & body fat (secondary outcome)	x		x	x	x	x	x	x
Questionnaires: ASES, VAS, PASS (secondary outcome)	x	x	x	x	x	x	x	x
Shoulder Range of Motion (secondary outcome)	x	x	x	x	x	x	x	x
Shoulder Strength (secondary outcome)	x	x	x	x	x	x	x	x

Table 1. Outline of pre- and postoperative timing of events and schedule of data collection.

Demographics.

Demographics of age, height, weight, race, arm dominance, and tear size and location will be recorded.

Inclusion and Exclusion Criteria.

The inclusion and exclusion criteria will be confirmed prior to enrolled, as described above in section 5.0.

Females of reproductive potential (women who have not been post-menopausal for at least 24 consecutive months, ie, who have had menses within the preceding 24 months, or women who have not undergone surgical sterilization, hysterectomy or bilateral salpingectomy or bilateral oophorectomy or tubal ligation) must have a negative serum or urine pregnancy test *with a sensitivity of ≤ 25 mIU/mL* within 48 hours prior to study entry.

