8.0 Criteria for Evaluation and Endpoint Definitions

Outcome Measures

The primary outcome measure will be rotator cuff healing as measured by the MRI Sugaya classification.^{6,7} Measures will be performed at 12 weeks (the conclusion of Oxandrolone vs. placebo treatment), 6 months, 1 year and 2 years follow-up. The primary end-point will be 6 months.

Secondary outcome measures will include:

- 1) MRI evidence of rotator cuff fatty infiltration and muscle volume.
- 2) Patient-reported outcomes will be assessed with the ASES, a VAS, and PASS questionnaire.
- 3) Functional outcome will be assessed with shoulder range of motion with goniometer and isometric shoulder strength measures using a handheld dynamometer
- 4) Lean body mass and fat will be assessed with bioelectric impedance.

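### Section 6.0 schedules liver enzymes at weeks 2, 6, 12 and 24, but the Table 1 row omits weeks 6 and 12; if Table 1 is followed, tests up to the end of dosing fall from three to one

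*Combined protocol and SAP*

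**What the plan says.** Section 6.0, under Patient Safety and Compliance, requires liver transaminases with the preoperative labs and adds: "Additionally, liver enzymes will be assessed at 2, 6, 12, and 24 weeks after rotator cuff repair". The same paragraph places the testosterone and oxandrolone assays before supplementation, then "at the 2 week post-operative visit and at the 6 month post-operative visit to assess for compliance". Its only stated response to a safety problem is general: the drug is stopped after an adverse reaction to it, and follow-up continues.

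Section 7.0 covers the testing visits, at which outcome and safety measures are collected, and says: "Dates and involved events are described in Table 1 below". In that table the row "Blood draw: Liver Enzymes", as read, is marked pre-procedure and at weeks 2, 24, 52 and 104. Weeks 6 and 12 are blank. The row directly above, "Blood draw: Testosterone level and Oxandrolone level", is marked pre-procedure and at weeks 2 and 24. The caption reads: "Table 1. Outline of pre- and postoperative timing of events and schedule of data collection".

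The Blood Draws paragraph later in section 7.0 refers back to what has already been described and names two purposes: watching for adverse effects and checking compliance. It gives no dates.

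Dosing starts on the day of surgery and lasts 12 weeks. Section 8.0 confirms that week 12 is the end of treatment: "Measures will be performed at 12 weeks (the conclusion of Oxandrolone vs. placebo treatment), 6 months, 1 year and 2 years follow-up".

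**The concern.** A coordinator working from Table 1 would draw no blood for liver enzymes at weeks 6 and 12. A coordinator working from section 6.0 would. The two differ during and at the end of drug exposure, which is when liver monitoring matters most.

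Three statements in the protocol give this weight. Section 6.0 says of earlier experience: "Elevated liver transaminase levels have been noted but have been transient and asymptomatic". If rises cause no symptoms, a blood test is the way to see them. Section 1.0 says that adverse events tend to depend on dose and to track duration of use, and the omitted tests fall in the later part of the course. Section 1.0 also says that the proposed dose has not been studied. In men it is 24 mg/day, against an approved maximum of 20 mg/day.

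Stopping the drug can help only while it is still being taken. A rise that is not detected until week 24 comes to light too late for that.

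**Working it through.** The plan gives no figure to reproduce here. The check is a count of scheduled tests.

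**Inputs.** Section 6.0, post-operative weeks: {2, 6, 12, 24}. Table 1 liver row, post-operative weeks: {2, 24, 52, 104}. Both include a preoperative test. Dosing: week 0 to week 12 (sections 6.0 and 8.0).

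**Where they differ.** Only in section 6.0: weeks 6 and 12. Only in Table 1: weeks 52 and 104. In common: weeks 2 and 24.

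| Quantity | Section 6.0 | Table 1 as read |
|---|---|---|
| Tests after surgery, up to and including week 12 | 3 (weeks 2, 6, 12) | 1 (week 2) |
| Tests before dosing ends (week < 12) | 2 (weeks 2, 6) | 1 (week 2) |
| Untested stretches within dosing, in weeks | 2 − 0 = 2; 6 − 2 = 4; 12 − 6 = 6 | 2 − 0 = 2; 12 − 2 = 10 |
| First test at or after the last dose | 12 − 12 = 0 weeks later | 24 − 12 = 12 weeks later |
| Post-operative tests after week 12 | 1 of 4 | 3 of 4 |

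These lines are different views of the same two blank cells and should not be added together.

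**Could another draw cover the gap?** Table 1 has two blood-draw rows. The testosterone and oxandrolone row is also blank at weeks 6 and 12, so no other scheduled draw would pick up the missing tests.

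**Is the row misread?** The table has eight columns: pre-procedure, procedure day, and weeks 2, 6, 12, 24, 52 and 104. The liver row has all eight cells. The testosterone and oxandrolone row above it (pre-procedure, 2, 24) agrees with its text in section 6.0, so the columns appear aligned there. Against that, moving the section 6.0 marks at weeks 6, 12 and 24 two columns to the right gives 24, 52 and 104, which is exactly what the row shows. A full set of cells does not prove that the content is right either: the MRI rows are also complete, yet they carry no week-24 mark although section 8.0 schedules a 6-month measurement. A displaced row is therefore possible but not shown.

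**Dose.** Men: 2 × 12 = 24 mg/day, above 20. Women: 2 × 6 = 12 mg/day, within 20.

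**The case against.** The strongest reply is that section 6.0 plainly governs. It is the dedicated safety section and its schedule is explicit, whereas the Table 1 caption describes only an outline. The Blood Draws paragraph points back to earlier text, and the purposes it names, safety and compliance, match the section 6.0 heading; Table 1 states no purpose for its draws. On that reading no test is lost. This carries weight: it would be wrong to say that the protocol gives no guidance at all. But the back-reference could equally take in Table 1, which also comes before it, and section 7.0 sends staff to that table for dates. The conflict is narrowed, not resolved.

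A second reply is that the row may be displaced, by the author or in reading the PDF. A reading error would remove the point. An author's slip would still need correcting. The source table has to be checked first.

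A reader might also infer that participants would lose a test that would have stopped their drug, or would come to harm. The documents do not support that. The two-times-normal limit is an entry criterion; there is no enzyme threshold during treatment, and nothing says that a symptom-free rise counts as an adverse reaction. Section 1.0 reports no serious hepatic toxicity with treatment of up to 3 months, even at doses up to 80 mg/day. The above-label argument covers men only.

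**Conclusion.** The two schedules conflict as written, and this should be fixed. If Table 1 is followed, liver tests through the end of the 12-week course fall from three to one, and tests before dosing ends fall from two to one. The last 10 weeks of dosing are then untested, and the next test is 12 weeks after the last dose. If section 6.0 is followed, the loss is zero. The documents do not show which schedule staff would use, so the effect lies between these two cases.

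The conclusion rests on the Table 1 row being as read, which is likely but not certain, and on week 12 being the end of dosing. That a missed test would change a decision to stop the drug is an inference through the general adverse-reaction rule. The efficacy analysis is not affected.

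**What to change.** First compare the liver row with the source Table 1. If weeks 6 and 12 are marked there, they need no edit. Otherwise:

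1. Mark weeks 6 and 12 in the Table 1 liver row.
2. Separately, make weeks 52 and 104 agree. Either delete them from Table 1, so that the row reads pre-procedure, 2, 6, 12, 24; or add them to section 6.0, so that the row reads pre-procedure, 2, 6, 12, 24, 52, 104.

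Step 1 alone does not bring the two places into agreement.

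The cost is two marks in one row, plus two deletions or one changed phrase in section 6.0. Relative to Table 1, weeks 6 and 12 add two draws per participant at visits that already exist; deleting weeks 52 and 104 removes two, which leaves the total unchanged at five including the preoperative test. Relative to section 6.0 there are no extra draws unless weeks 52 and 104 are kept, in which case there are two.

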There are many predisposing factors that may prompt rotator cuff healing failure or re-tear. These factors can be divided into patient-specific factors (patient age, gender, body-mass index (BMI), smoking status, and comorbidities) and tear-specific factors (tear pattern, tear size, and tear chronicity).^{23,24} The major biologic sequelae of a constellation of both patient- and tear-specific factors are the changes to the muscle-tendon unit.^{7,25} The hallmarks of these changes are muscle atrophy, fatty infiltration, and intercellular fibrosis of the torn rotator cuff muscle-tendon unit.^{7,25} These changes begin at the time of the tear and currently go largely unaddressed at the time of repair.

Researchers have pursued biologic augmentation at the time of arthroscopic rotator cuff repair; however, time-zero modifications to the healing interface with growth factors, platelet-rich plasma, and stem cells have failed to address the hallmarks of the biologic problem (muscle atrophy, fatty infiltration, and intercellular fibrosis).²⁶ Therefore, these modalities in both preclinical and clinical models have failed to consistently demonstrate improvements in healing rates, re-tear rates, functional results, or patient satisfaction.²⁷⁻²⁹ Recently, researchers have attempted to address the biologic hallmarks of rotator cuff tearing with a series of animal studies examining the effects of anabolic steroids on rotator cuff healing.^{25,30,31} This line of preclinical studies demonstrated that anabolic steroids, when administered as an adjuvant to rotator cuff repair, can halt the progression of fatty infiltration, decrease muscle atrophy, and promote rotator cuff healing.

Despite the wide range of doses in controlled clinical trials, our proposed dose has not been studied. The drug manufacturer, Gemini Labs LLC, is providing the drug in 6mg doses for the study and the proposed oxandrolone dose in men is 24mg/day. Currently, the FDA-approved dose in adults is up to 20mg/day, usually in two to four divided doses. Most controlled studies use doses of 5–20mg/day.^{3,36} In patients with moderate to severe alcoholic hepatitis, however, doses have been given up to 80mg/day.³⁷ Adverse events are typically dose-dependent and correlate to the duration of use.³⁶ Serious hepatic toxicity has not been shown with short term (≤ 3 months) treatment of oxandrolone, even with up to 80mg/day.^{36,37}

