- Fluid and Electrolytes: Retention of serum electrolytes (sodium chloride, potassium, phosphate, calcium).
- Musculoskeletal: Premature closure of epiphyses (in children).
- Dermatologic: Acne (especially in females and prepubertal males), hirsutism and male pattern baldness in females.
- Patients with moderate to severe COPD or COPD patients who are unresponsive to bronchodilators should be monitored closely for COPD exacerbation and fluid retention.

Contraindications: nephrosis, carcinoma of breast or prostate, hypercalcemia, pregnancy

US Boxed Warning:

Peliosis hepatitis: A condition in which liver, and sometimes, splenic tissue is replaced with blood-filled cysts which has occurred in patients receiving androgenic anabolic steroids. These cysts may be associated with hepatic dysfunction and even liver failure. This condition is usually completely reversible with cessation of drug.

Protocol Number: APP-17-01020

Version Date: 9/1/2017

Liver cell tumors: Most often benign and androgen-dependent, however, fatal malignant tumors have occurred. Withdrawal of the drug often results in regression or cessation of tumor progression. Hepatic tumors associated with androgens and anabolic steroids are much more vascular than other hepatic tumors and may be silent until life-threatening, intra-abdominal hemorrhage develops.

Blood Lipid Changes: Changes associated with increased risk of atherosclerosis are seen in patients treated with androgens or anabolic steroids, including decreased high-density lipoprotein (HDL) and increased low-density lipoprotein (LDL).

Pregnancy: Oxandrolone is classified as Category X in pregnancy due to teratogenic effects including embryotoxicity, fetotoxicity, infertility, and possible masculinization of the fetus.

Breast Feeding: It is unknown whether Oxandrolone is excreted in human milk. Because of the potential of serious adverse reactions in nursing infants from Oxandrolone, women who are nursing and do not wish to stop may not take part in the study.

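### Table 1 as read leaves out the week 6 and week 12 liver tests that Section 6.0 promises, and no HDL or LDL test is scheduled although the protocol lists lipid change under its boxed warning

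*Combined protocol and SAP*

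**What the plan says.** Section 6.0 (Patient Safety and Compliance) has transaminases measured with the pre-operative labs and continues: "Additionally, liver enzymes will be assessed at 2, 6, 12, and 24 weeks after rotator cuff repair". It also says that the drug is stopped after any adverse reaction, with outcome follow-up continuing.

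Section 7.0 sends the reader to Table 1 for dates and events. The row "Blood draw: Liver Enzymes", as read, is marked pre-procedure and at weeks 2, 24, 52 and 104, with nothing at weeks 6 or 12. The same section states: "Outcome measures and safety measures will be collected at routine postoperative visits with the operating surgeon".

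Section 4.0, under its US Boxed Warning heading, includes blood lipid changes: "Changes associated with increased risk of atherosclerosis are seen in patients treated with androgens or anabolic steroids". It names a fall in HDL and a rise in LDL.

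On dose, Section 1.0 is open: "Despite the wide range of doses in controlled clinical trials, our proposed dose has not been studied", and "Currently, the FDA-approved dose in adults is up to 20mg/day, usually in two to four divided doses". It adds: "Adverse events are typically dose-dependent and correlate to the duration of use". The dose in Section 6.0 is 12 mg twice daily for men and 6 mg twice daily for women, for 12 weeks from the day of surgery.

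**The concern.** There are two separate gaps.

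The first is a conflict between two statements of one safety schedule. If the table is the working document, liver enzymes are sampled once during treatment, at week 2. The next sample, at week 24, comes 12 weeks after the last dose. Section 6.0 describes earlier transaminase rises as transient and without symptoms. A later rise of that kind could come and go between the two samples, and no symptom would lead anyone to stop the drug.

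The second is that an effect the protocol itself ranks among the boxed warnings is not measured, although blood is drawn anyway. A healing benefit in patients aged 40 to 75 would then be reported with no lipid data to set against it.

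**Working it through.** **Dose.** Section 6.0 gives men 12 mg × 2 = 24 mg/day, which reproduces the figure in Section 1.0. Against the quoted limit, 24/20 = 1.20. For women, 6 mg × 2 = 12 mg/day, and 12/20 = 0.60.

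**Schedules side by side** ("x" = planned; 6 months, 1 year and 2 years are shown as weeks 24, 52 and 104).

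| Item and source | Pre | 2 | 6 | 12 | 24 | 52 | 104 |
|---|---|---|---|---|---|---|---|
| Liver enzymes, Section 6.0 | x | x | x | x | x | | |
| Liver enzymes, Table 1 | x | x | | | x | x | x |
| Testosterone and oxandrolone, Section 6.0 | x | x | | | x | | |
| Testosterone and oxandrolone, Table 1 | x | x | | | x | | |
| MRI, Section 8.0 | not listed | | | x | x | x | x |
| MRI, Table 1 | x | | | x | | x | x |

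**Liver draws.**
- Total per patient: 5 in Section 6.0 and 5 in Table 1.
- In the dosing period (weeks 0 to 12): 3 in Section 6.0 (weeks 2, 6, 12) and 1 in Table 1 (week 2).
- Early enough to prompt stopping: 2 in Section 6.0 (weeks 2 and 6) and 1 in Table 1. Week 12 is when dosing ends, so that draw gives the end-of-treatment value but cannot shorten exposure.
- Position of week 2: 2 × 7 = 14 of 12 × 7 = 84 dosing days. Under the table, 12 − 2 = 10 of the 12 dosing weeks follow the last on-treatment sample.
- Time from last dose to the later draws: 24 − 12 = 12, 52 − 12 = 40 and 104 − 12 = 92 weeks. The two draws that only the table has are the least informative about a 12-week drug.

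**Is the table read correctly?** The liver row has all its cells, and the other blood-draw row agrees with Section 6.0, so a simple column shift looks unlikely. Against that, the liver row has five marks, the same number that Section 6.0 implies, so misplaced marks are possible. The MRI rows omit 6 months, which Section 8.0 makes the primary end-point. Table 1 therefore differs from the text in more than one place.

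**Lipids.** Sections 6.0 and 7.0 name three kinds of blood test: testosterone, oxandrolone and liver enzymes. Section 3.0 (Feasibility) mentions safety laboratory tests, and Section 7.0 (Blood Draws) mentions monitoring for adverse effects; neither names a further analyte. Scheduled HDL or LDL tests: 0. This count rests on the whole text available, not on the table. The part following the Key Personnel heading in Section 3.0 was not available; a lipid schedule there is unlikely but cannot be excluded.

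**The case against.** The best defence is that Section 6.0 is the explicit safety section and leaves no doubt about the weeks. The caption of Table 1 calls it an outline, it is visibly incomplete elsewhere (it also has no row for the monthly pregnancy test in Section 3.0), and nothing shows that staff would follow it over Section 6.0. This stands: the liver point is a clerical conflict to be settled, conditional on the table being both correctly read and followed. It is not evidence that on-treatment monitoring will be skipped. It still deserves correction, because Section 7.0 sends readers to the table for dates.

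The sponsor also offers safety reassurance: no serious liver toxicity in short-term use up to 80 mg/day, no androgenic effects in earlier studies, and no long-term adverse events in trauma patients and healthy men. The first two concern other organ systems, and the last is general; none names lipids. The exclusions for heart failure, recent infarction and uncontrolled hypertension lower cardiovascular risk but measure nothing.

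A reader might infer that the men's dose is itself the fault. The documents do not support that. The dose and its relation to the approved limit are disclosed, and the lipid gap would exist at 20 mg/day too; the higher, unstudied dose only makes it more relevant in men.

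A reader might also want the share of liver rises missed, or the lipid difference the trial could detect. The documents give no event rate, onset, duration or lipid SD, so such figures would depend on whatever was assumed, and none is offered.

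Finally, the absence of liver enzymes from the outcome list in Section 8.0 might look like an error. It is not: safety laboratory values can be monitored clinically without being modelled as outcomes.

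**Conclusion.** Both gaps hold, as a cheap improvement. On liver enzymes, the text and Table 1 as read disagree at four visits: weeks 6 and 12 are missing from the table, and weeks 52 and 104 are added. If the table governs, the dosing period has 1 sample instead of 3, and 1 instead of 2 that could prompt an early stop. This assumes that the table was read correctly, which the original can settle. More draws do not by themselves ensure action, since Section 6.0 gives no enzyme threshold for stopping.

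On lipids, no HDL or LDL test is scheduled in the text available, for an effect listed under the protocol's own boxed-warning heading. Twelve weeks of treatment is short, so lasting lipid harm may be small; the loss is mainly of information. Neither gap touches the primary efficacy analysis.

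**What to change.** 1. Check the original Table 1. If it reads as above, correct the liver row to pre-operative and weeks 2, 6, 12 and 24, as in Section 6.0. Draws stay at 5 per patient; keeping weeks 52 and 104 as well is optional. If the table is now being followed, this adds 2 × 116 = 232 draws, and dropping weeks 52 and 104 removes 232. If Section 6.0 is already followed, no draws are added. Check the missing 6-month MRI mark at the same time.

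2. Run HDL and LDL on those same five samples, and summarise lipids and liver enzymes by arm, on treatment and at week 24.

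3. Keep these results from the operating surgeon and the outcome assessors. The oxandrolone assay reveals the arm more directly than lipids would and needs a restricted reporting route anyway; the same route can serve both.

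The cost is a protocol amendment, up to 116 × 5 = 580 lipid assays (104 × 5 = 520 at the number before the attrition allowance), and a small unblinding risk that restricted reporting limits. No new visit is needed, since weeks 2, 6, 12 and 24 are already study visits.
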